7.2.4 Visit 4 (Clinic visit or phone Visit-6 months after IUD insertion)

At 6 months subjects will be scheduled to return to REI clinic to have an IUD string check and if no strings are visualized then this will be categorized as malposition and the investigator will continue with routine care and work up Subjects who return to clinic for Visit 4 will also have a transvaginal ultrasound performed.

If the subject does not present for a clinic follow up, then she will be contacted by the Study Coordinator or investigator via phone to see if they still have their IUD in place (and when it was removed or lost).

All subjects will be surveyed for pain with the VAS and any adverse events (including abnormal uterine bleeding) will be recorded. All subjects will be asked to categorically rate their satisfaction with the IUD on a Likert Scale.

7.3 Duration of Participation

The total amount of time for participation in the study is 6 months.

8.0 Subject Numbers and Statistical Plan

8.1 Number of Subjects

The sample will consist of 376 women who are undergoing scheduled IUD insertion, thereby 188 women per arm.

8.2 Sample size determination

The sample will consist of 376 women who are undergoing scheduled IUD insertion. We assume a discontinuation rate of 23% at 6 months for the traditional IUD insertion method based on a large study of experienced clinicians inserting IUDs and a large Cochrane review [2, 3]. We project that the ultrasound guided IUD insertion will have half the discontinuation rate, i.e., it will be 11.5% (due to the correct placement of the IUD in the fundus). A sample size of 338 (169 per group) will provide 80% power to detect a difference in the discontinuation proportions at 6 months of 0.23 in the traditional IUD insertion arm and 0.115 in the ultrasound guided arm using a two-sided test having a significance level of 0.05. However, we anticipate 10% subject dropout for this longitudinal study; therefore, we will enroll a total of 376 subjects.

8.3 Statistical methods

The primary analysis will use an intent-to-treat approach to examine differences in the discontinuation rates in the two treatment arms. A modified Poisson regression approach will be used to compare the treatment arms with respect to the primary outcome of IUD discontinuation [4] . An advantage of this method is that it will provide an estimate of the risk ratio and associated 95% confidence interval for this prospective study as well as providing the flexibility to adjust the analysis for potentially confounding factors (e.g., age at IUD insertion). As a secondary analysis, the Kaplan-Meier survival analysis method will be used to assess time from IUD insertion until IUD discontinuation with the comparison between the two treatment arms performed using the log-rank test. For the Kaplan-Meier analysis, the data from a specific subject will be censored at 6 months if the IUD was still in place at 6 months or it will be censored at the time of subject dropout if the subject dropped out of the study prior to 6 months. We plan on performing an interim analysis to assess efficacy of the intervention around the midpoint of the study.

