1.2 Primary Study Endpoints

IUD discontinuation rate at 6 months

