7.2.3 Visit 3 (4-6 weeks after Visit 2) Subjects will be scheduled to return to REI clinic 4-6 weeks after insertion of the IUD as routine follow-up. Subjects will be asked about any adverse events. Subjects will be asked to complete the Likert scale to indicate their satisfaction level with their IUD and the Visual Analogue Scale to indicate their level of pain. A routine string check in the form of a speculum exam will be performed in addition to a transvaginal ultrasound to confirm positioning of the IUD. If malposition is determined, then routine care will be to remove the IUD. The ultrasound operator will be blinded to the subject's arm in the study

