16.2 Feasibility of recruiting the required number of subjects

All women undergoing a scheduled IUD insertion will be offered participation in the study when checking in at the Hershey Medical Center or one of the Penn State outpatient clinic sites, which total an average of 750 IUD insertions annually.

In terms of recruitment, this will be a randomized controlled, single center, prospective, clinical trial. We anticipate enrolling 7-8 women per week over a one year enrollment period. A total of 1.5 years will be required to complete the study after start up; 12 month enrollment period, 6 month observation period.

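### The interim efficacy look in section 8.3 has no boundary, final level, consequence or defined timing, so the two-sided 0.05 in section 8.2 is not protected

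*Combined protocol and SAP*

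**What the plan says.** The only text on the look is the last sentence of section 8.3: "We plan on performing an interim analysis to assess efficacy of the intervention around the midpoint of the study". That section names two analyses of discontinuation: a modified Poisson regression giving a risk ratio (primary) and a Kaplan-Meier/log-rank comparison (secondary). It does not say which of them the look uses.

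Section 8.2 sizes the trial "using a two-sided test having a significance level of 0.05", with the result that "A sample size of 338 (169 per group) will provide 80% power". No allowance for a second test appears there.

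The primary endpoint in section 1.2 is "IUD discontinuation rate at 6 months", so a woman who keeps her device contributes a final outcome only after six months. On timing, section 16.2 says: "We anticipate enrolling 7-8 women per week over a one year enrollment period", and "A total of 1.5 years will be required to complete the study after start up; 12 month enrollment period, 6 month observation period".

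Section 10.0 states that a DSMB does not apply, so no board or charter exists that could supply the missing rule.

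**The concern.** The stated purpose of the look is efficacy, so it cannot be read as a safety or feasibility check. A look that can support an efficacy claim uses part of the 5% error allowance, and the plan neither divides that allowance nor says that no claim can follow. Control of false positives for the primary conclusion therefore depends on a rule that is not written. A rule chosen after interim data have been seen could not be defended as pre-specified.

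The undefined trigger is a second, smaller gap. It leaves open how much information the look contains and which women are in it. Analysing whoever happens to have a known outcome would distort the rates, because a removal is known when it happens while continuation is known only at six months.

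**Working it through.** **1. The plan's own sample size.** Inputs from section 8.2: p1 = 0.23, p2 = 0.115, two-sided 0.05, 80% power, 10% dropout. With pooled variance under the null, p̄ = (0.23 + 0.115)/2 = 0.1725 and

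n = [1.960·√(2·0.1725·0.8275) + 0.8416·√(0.23·0.77 + 0.115·0.885)]² / 0.115²
= (1.0472 + 0.4444)² / 0.013225 = 168.2, rounded up to 169 per arm.

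Power at 169 per arm is 80.2%, and 338/0.9 = 375.6, rounded up to 376. Both figures in the plan reproduce, as a design with one test and no interim look.

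**2. Type I error with two looks, normal theory.** With a fraction t of the outcomes at the interim, the two test statistics are bivariate normal with correlation √t, and

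overall error = 1 − P(|Z1| < c1 and |Z2| < c2).

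| Rule | t | Overall error |
|---|---|---|
| p<0.05 at both looks | 0.50 | 8.3% |
| p<0.05 at both looks | 0.25 | 9.1% |
| O'Brien-Fleming, c2 = 1.977, c1 = 1.977/√0.5 = 2.797 (p<0.0052, then p<0.0480) | 0.50 | 5.00% |
| The same O'Brien-Fleming p-values | 0.25 | 5.16% |
| Haybittle-Peto (p<0.001, then p<0.05) | 0.50 | 5.02% |

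**3. The same with the planned type of test.** One million simulated trials with 169 per arm, testing Z = ln(a/b) / √(1/a − 1/n + 1/b − 1/n), where a and b are the events in the two arms and n is the number per arm. This is the unadjusted risk ratio with the modified Poisson robust variance. The second null rate, 17.25%, is the mean of the two design rates.

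| Rule | Null rate | Look at 84 per arm | Look at 42 per arm |
|---|---|---|---|
| Single final test | 23% | 4.7% | 4.7% |
| p<0.05 at both looks | 23% | 7.6% | 7.7% |
| p<0.05 at both looks | 17.25% | 7.4% | 7.2% |
| p<0.05 at both, only benefit claimable early | 23% | 6.1% | 6.2% |
| O'Brien-Fleming | 23% | 4.6% | – |
| Haybittle-Peto | 23% | 4.7% | – |

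The single final test has no interim look, so its two entries are the same figure.

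**4. What midpoint could mean.** Assume uniform accrual of 376 over 12 months, or 31.3 a month. The 7-8 a week in section 16.2 gives 364-416 over 52 weeks.

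| Reading | Month | Enrolled | With 6-month outcome due |
|---|---|---|---|
| Half enrolled | 6 | 188 | 0 (0%) |
| Half of the 18 months | 9 | 282 | 94 (25%) |
| Half of the outcomes | 12 | 376 | 188 (50%) |

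**5. Using only women with a known outcome at month 12.** Assume 188 per arm, removals spread evenly over six months and no dropout. The first 94 per arm are complete. From the second 94, on average half of the eventual removals are already known.

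- Traditional arm: removals 94·0.23 + ½·94·0.23 = 21.6 + 10.8 = 32.4; known 94 + 10.8 = 104.8; apparent rate 30.9% instead of 23%.
- Ultrasound arm: removals 10.8 + 5.4 = 16.2; known 94 + 5.4 = 99.4; apparent rate 16.3% instead of 11.5%.

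**6. Performance under 23% against 11.5%** (risk-ratio test, look at 84 per arm).

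- Chance of crossing at the interim: 47.8% at p<0.05, 13.4% with O'Brien-Fleming, 2.9% with Haybittle-Peto.
- Overall power: single look 80.1%, O'Brien-Fleming 79.4%, Haybittle-Peto 80.1%. By normal theory, O'Brien-Fleming gives 79.9% against 80.2%.
- Median risk ratio (true value 0.50): 0.375 among interim results with p<0.05, 0.467 among significant results from a single final look, 0.435 among significant results from two unadjusted looks.

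**The case against.** The plan does not say that the trial would stop, that a claim would be made early, or that 0.05 would be used at the interim. What is shown is an unwritten rule, not an inflated error rate. This is right as far as it goes, and the inflated figures above are conditional for that reason. But the plan does not say that the look is descriptive either, and it calls its purpose efficacy. An error rate that depends on a choice still to be made is not protected.

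The normal-theory 8.3% and 9.1% overstate the worst case for the planned test, where 7.6-7.7% is the better figure, and 6.1-6.2% if only benefit can be claimed early. That stands.

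Timing hardly moves the error rate (7.6% against 7.7% at a 23% null rate), and at the 0% reading no test of the 6-month outcome would be possible. That also stands. The trigger matters for reproducibility and for who is analysed. It is secondary to the missing rule.

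Finally, a strict boundary is not automatically exact. Haybittle-Peto with a final 0.05 gives 5.02%, and O'Brien-Fleming levels worked out for 50% information give 5.16% if used at 25%. These excesses are small, but they show that the levels must be tied to a stated trigger.

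**Conclusion.** The concern holds and should be fixed before any interim data are examined. Section 8.3 commits to an efficacy look without a test, boundary, final level, consequence or defined time, while section 8.2 spends the full two-sided 0.05 once.

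If 0.05 is used at both looks and either can support a claim, overall type I error is about 7.6% with the planned risk-ratio test and the look at half the outcomes, against 4.7% for a single look. With a strict boundary at that point, or a look from which no claim can follow, it is about 5% or slightly less. Exaggeration of the effect estimate is a lesser matter: the median significant risk ratio moves from 0.467 to 0.435.

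These figures assume one look at 25% or 50% of outcomes, 169 evaluable women per arm and an unadjusted analysis. The timing figures also assume uniform accrual. The sample size itself is correct as a single-look calculation.

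**What to change.** Choose one of the following and write it into section 8.3.

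- **Delete the efficacy look.** The 0.05 and 80% in section 8.2 are then true as written. Little is lost. On the planned 12-month accrual, a look at half the outcomes falls when enrolment is due to be complete, and under the design effect a strict boundary would be crossed early only about 13% (O'Brien-Fleming) or 3% (Haybittle-Peto) of the time. If accrual took 18 months (an assumption), 376/18 = 20.9 women a month, the first 188 would be complete at month 15 and about 63 women would still be to enrol.
- **Keep it as a descriptive look.** State that no efficacy claim or early stop can follow from it.
- **Keep it as an efficacy look, with a rule.** State:
  1. The test is the 6-month discontinuation risk ratio in the first 188 women randomised (188 × 0.9, about 169 after dropout), run once all of them have reached six months after insertion. It does not use whichever women have a known outcome.
  2. The boundary, for example O'Brien-Fleming (p<0.0052 interim, p<0.0480 final) or Haybittle-Peto (p<0.001 interim, p<0.05 final; a final 0.0498 gives exactly 5% by normal theory).
  3. What a crossing leads to.

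  Then restate alpha and power in section 8.2 to match.

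Having the look run by someone who does not enrol or treat subjects is good practice, but type I error control does not depend on it.

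The cost is one paragraph in 8.3 and one sentence in 8.2. O'Brien-Fleming at the planned size loses 0.3 points of power by normal theory, or 0.7 with the risk-ratio test. Holding 80% by normal theory would take 171 per arm, so 342/0.9 = 380 enrolled instead of 376. Haybittle-Peto costs essentially no power.

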9.0 Confidentiality, Privacy and Data Management

See the Research Data Plan Review Form

10.0 Data and Safety Monitoring Plan

Abdominal ultrasound is minimal risk and it is not plausible that this intervention would worsen outcomes. The only plausible anticipated risks relate to the risks inherent in the insertion of the IUD. Therefore a DSMB is not applicable for this study.

11.0 Risks

The primary risk to the subject is loss of confidentiality of their private medical information.

Risk of Randomization

Ultrasound: ultrasound is a safe procedure that uses low-power sound waves. There are no known risks. Although ultrasound is a valuable tool, it has limitations. Sound doesn't travel well through air or bone, so ultrasound isn't effective at imaging parts of your body that have gas in them or are hidden by bone. There is a risk of incidental findings while performing the ultrasound, these will be noted in the chart documentation and followed by your physician as needed. There is no known risk with transabdominal ultrasound.

Standard of Care: Discomforts associated with IUD include: placement discomfort, missed menstrual periods, cysts on the ovary, headache/migraine, acne, depressed mood, heavy or prolonged menstrual bleeding, vaginal discharge, breast tenderness, nausea, nervousness, inflammation of cervix, vulva, or vagina, pelvic pain during period, back pain, weight increase, decreased sex drive, pain during intercourse, anemia, unusual hair growth or loss, skin irritations, feeling bloated, swelling of hands and feet, and expulsion. Some serious but uncommon side effects of IUD include: pelvic inflammatory disease, sepsis, and perforation in the event IUD becomes attached to or goes through the wall of the uterus, which may require surgery.

12.0 Potential Benefits to Subjects and Others

12.1 Potential Benefits to Subjects

The possible benefit a subject may experience is greater satisfaction and lower IUD discontinuation rates when insertion is performed with the ultrasound guided insertions method compared to the traditional blind insertion.

12.2 Potential Benefits to Others

Other women will benefit from the knowledge gained by this new method of IUD insertion. Ultrasound guided insertion could lead to more accurate placement of the IUD, less pain, and better satisfaction with the procedure.

13.0 Sharing Results with Subjects

Not applicable.

14.0 Subject Stipend (Compensation) and/or Travel Reimbursements

A travel stipend of \$25 will be given to subjects at the 6 month follow up visit.

15.0 Economic Burden to Subjects

15.1 Costs

There are no research-related costs to the subjects for their participation in this study except in the following situation:

Subjects who experience signs and symptoms related to their IUD or have a malpositioned IUD at their 4-6 week visit will have standard of care initiated and either the subject or the subject's insurance company will be responsible for the costs associated with that standard of care treatment.

15.2 Compensation for research-related injury

It is the policy of the institution to provide neither financial compensation nor free medical treatment for research-related injury. In the event of injury resulting from this research, medical treatment is available but will be provided at the usual charge. Costs for the treatment of research-related injuries will be charged to subjects or their insurance carriers.

16.0 Resources Available

16.1 Facilities and locations

All research recruitment and procedures will take place in the Women's Health clinic at the Hershey Medical Center or one of the Penn State outpatient clinic sites.

16.2 Feasibility of recruiting the required number of subjects

All women undergoing a scheduled IUD insertion will be offered participation in the study when checking in at the Hershey Medical Center or one of the Penn State outpatient clinic sites, which total an average of 750 IUD insertions annually.

In terms of recruitment, this will be a randomized controlled, single center, prospective, clinical trial. We anticipate enrolling 7-8 women per week over a one year enrollment period. A total of 1.5 years will be required to complete the study after start up; 12 month enrollment period, 6 month observation period.

16.3 PI Time devoted to conducting the research

[name] is extremely committed to her research and she is familiar with research at this location and the local culture. She has been a PI or a co-investigator on greater than 20 IRB approved research protocols. [name] sees patients 3 days a week with one day of OR time. When not in clinic, time can be devoted to research projects or seeing study patients.

16.4 Availability of medical or psychological resources

Medical resources will already be available since the participants will be having the procedure in clinic under the care of a physician or licensed nurse practitioner.

16.5 Process for informing Study Team

The PI will communicate via email as main method of communication with the study team.

CITI Training

The investigators and all staff involved in the study will have completed their required Collaborative IRB Training Initiative (CITI) in the protection of human research subjects.

Protocol Procedure Training

Study staff delegated to conduct specific study procedures will be trained on these procedures individually or in a group format. Delegation of responsibility will be documented on the Delegation of Responsibility Log and updated as indicated.

The physician investigators are all trained in IUD insertion and routinely perform the IUD insertion procedure.

17.0 Other Approvals

17.1 Other Approvals from External Entities

Not applicable

17.2 Internal PSU Committee Approvals

Check all that apply:

- Anatomic Pathology – Hershey only – Research involves the collection of tissues or use of pathologic specimens. Upload a copy of HRP-902 - Human Tissue For Research Form on the “Supporting Documents” page in CATS IRB. This form is available in the CATS IRB Library.
- Animal Care and Use – All campuses – Human research involves animals and humans or the use of human tissues in animals
- Biosafety – All campuses – Research involves biohazardous materials (human biological specimens in a PSU research lab, biological toxins, carcinogens, infectious agents, recombinant viruses or DNA or gene therapy).
- Clinical Laboratories – Hershey only – Collection, processing and/or storage of extra tubes of body fluid specimens for research purposes by the Clinical Laboratories; and/or use of body fluids that had been collected for clinical purposes, but are no longer needed for clinical use. Upload a copy of HRP-901 - Human Body Fluids for Research Form on the “Supporting Documents” page in CATS IRB. This form is available in the CATS IRB Library.
- Clinical Research Center (CRC) Advisory Committee – All campuses – Research involves the use of CRC services in any way.
- Conflict of Interest Review – All campuses – Research has one or more of study team members indicated as having a financial interest.

- Radiation Safety – Hershey only – Research involves research-related radiation procedures. All research involving radiation procedures (standard of care and/or research-related) must upload a copy of HRP-903 - Radiation Review Form on the “Supporting Documents” page in CATS IRB. This form is available in the CATS IRB Library.
- IND/IDE Audit – All campuses – Research in which the PSU researcher holds the IND or IDE or intends to hold the IND or IDE.
- Scientific Review – Hershey only – All investigator-written research studies requiring review by the convened IRB must provide documentation of scientific review with the IRB submission. The scientific review requirement may be fulfilled by one of the following: (1) external peer-review process; (2) department/institute scientific review committee; or (3) scientific review by the Clinical Research Center Advisory committee. NOTE: Review by the Penn State Hershey Cancer Institute Scientific Review Committee is required if the study involves cancer prevention studies or cancer patients, records and/or tissues. For more information about this requirement see the IRB website at: <http://www.pennstatehershey.org/web/irb/home/resources/investigator>

18.0 Multi-Site Research

Not applicable

19.0 Adverse Event Reporting

19.1 Reporting Adverse Reactions and Unanticipated Problems to the Responsible IRB

Research subjects will be questioned about adverse events by the investigators at study visits 2, 3, and 4 or from the patient record if the patient calls or comes to the clinic or emergency room with a possible adverse event.

In accordance with applicable policies of The Pennsylvania State University Institutional Review Board (IRB), the investigator will report, to the IRB, any observed or reported harm (adverse event) experienced by a subject or other individual, which in the opinion of the investigator is determined to be (1) unexpected; and (2) probably related to the research procedures. Harms (adverse events) will be submitted to the IRB in accordance with the IRB policies and procedures.

20.0 Study Monitoring, Auditing and Inspecting

20.1 Auditing and Inspecting

The investigator will permit study-related monitoring, audits, and inspections by the Penn State quality assurance program office(s), IRB, the sponsor, and government regulatory bodies, of all study related documents (e.g., source documents, regulatory documents, data collection instruments, study data etc.). The investigator will ensure the capability for inspections of applicable study-related facilities (e.g., pharmacy, diagnostic laboratory, etc.).

21.0 Future Undetermined Research: Data and Specimen Banking

21.1

Not applicable

